# Active-Control Intervention: Remote Walking Program Description

(Prescribed walking program of 15 hours total over six weeks + concurrent use of SAM device 4 days during early training)

**Overview:** The Active-Control Intervention is similarly structured as Amped-PD Intervention, with the only exception of not using RAS/ music-based device. Participants will be instructed to complete five home/community-based walking sessions per week (one session/ day, 30 minutes in duration) for six weeks.

**Description of Walking Sessions:** Without using the music-based device, participants will conduct the walking sessions at their self-selected pace in a home/community environment. All other considerations as outlined above apply to this intervention.

**Duration of Walking Session:** Each individual walking session will be completed within a 30- minute timespan (i.e., should not be split up throughout the day. Participants will be asked to use their own wristwatch,

timer, or cellphone to monitor the time/ duration of walking session. Participants are allowed to rest as needed during the 30-minute training period.

**Walking program diary:** Participants will be asked to record in a study diary their schedule (dates and times) of walking, location, record of any falls they experience and any comments/issues they experience while performing the walking program.

**Safety Considerations:** Same as above as outlined in Amped-PD. **Physical therapy check-in call:** Same as above as outlined in Amped-PD. **Step Activity Monitoring:** Same as above as outlined in Amped-PD.

Interruptions in training: In the event of unavoidable interruptions in training, booster sessions may be implemented to promote treatment fidelity. For training interruptions that last up to 2 weeks, the participant will continue the program and receive booster sessions at 100% of the time missed. For training interruptions of greater than 2 weeks, the training will be restarted after a reasonable washout interval, as determined by the Principal Investigator (a licensed physical therapist). If training interruption resulted in permanent change in eligibility, the participant will be withdrawn from the study.

# 3. Second Evaluation Visit: Post-Assessment Visit (approximately 2-3 hours):

The post-intervention assessment visit will be scheduled within approximately 7 days of completion of the structured walking program and take place at the Center for Neurorehabilitation at Boston University. This visit will entail the same battery of assessments performed at Baseline Assessment including: 10MWT, 6MWT, Borg's RPE, Mini BESTest, MDS-UPDRS I/II/III, 5xSTS, PDQ-39, SRHI, GDS. Quantification of movement will be performed using wearable sensors to measure balance and walking as examined in the aforementioned battery of assessments.

Further, a usability questionnaire will be administered for those who completed Amped-PD. For both Amped-PD and Active-Control groups, participants will be asked to bring in their study diary for study personnel to review and to make a copy for their data file. This study diary will be returned to the participant for continued use if needed during the Follow-up Period. For the Amped-PD group, they will have continued access to the music-based device during the Follow-up Period. The SAM monitor will be given to the participant to wear for 7 days during Follow-Up Training. Participants who withdraw or are withdrawn prior to completing their last walking session may be asked to complete closing visit activities, if feasible.

4. Follow-Up Walking Program (2 weeks): Extended Remote Walking Program

Description for both groups (recommended continuation of routine walking + concurrent use of SAM device 4 days during follow-up training)

**Overview:** Participants in both Amped-PD and Active-Control groups will be recommended to carry out the walking program independently for another 2 weeks,

with walking duration and amount similar to that of the 6-week Remote Walking program (i.e. 30 min/ session x 5x/week). This recommendation to continue the walking program is similar to the common practice of a home exercise program that is recommended after discharge from an episode of physical therapy care. The main difference in this Follow-up Training relative to the prior Remote Walking Program is that this Follow-up Training is completely self-managed by the participants, where participants will naturally make choices on how they will continue and adhere with the recommended balance and walking as examined in the aforementioned battery of assessments. For both Amped-PD and Active-Control groups, participants will be asked to bring in their study diary for study personnel to review and to make a copy for their data file. For participants in the Amped-PD, they will return the music-based device to the research team.

**Step Activity Monitoring:** The participant will wear the SAM for 4 days after this final assessment visit. Once completed, the participant will return the SAM to study personnel via a pre-labeled addressed mailing envelope which will be provided to them during the final assessment. The researchers will download the data and will store in a secure server.

## **Statistical Analysis Plan**

We will use parametric statistics to data with normal distribution verified using Shapiro-Wilk test and to data that meet the assumptions of homogeneity of variances using Levene's test. Otherwise, non-parametric statistics will be used.

To examine between-group differences for all primary outcomes (moderate intensity minutes, daily steps, stride time variability, and habit strength), we will run a one-way ANOVA or Kruskall-Wallis test to compare change scores at the 6-Week and 8-Week clinical assessments relative to baseline.

To examine within-group differences for all primary outcomes (moderate intensity minutes, daily steps, stride time variability, and habit strength), we will run a Repeated Measures ANOVA or Friedman's ANOVA on absolute values of all primary outcomes across their respective timepoints, with multiple post-hoc comparisons corrected using Bonferroni adjustments.

For all secondary outcomes, we will perform between-group analyses using non-parametric statistics to compare change scores at the 6-Week and 8-Week clinical assessments relative to baseline, using two-tailed tests with alpha set at 0.05.

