# **Study Protocol**

# **Study Design:**

The study is a parallel community-based 2-arm randomized controlled trial (RCT) in which the study evaluations will take place at the Center of Neurorehabilitation (CNR) at Sargent College, Boston University. We will enroll 44 community-dwelling adults ages 40-80 yrs with idiopathic PD of mild to moderate disease severity, who are independent community ambulators. We will exclude those with atypical PD, have significant freezing of gait, have history of falls in the past 3 months, have a comfortable walking speed <0.4 m/s, and significant cognitive or hearing impairments. Eligible participants will be randomly allocated to either

[figure not shown]

Figure 1 Study flow. Abbreviations: CoV: Coefficient of Variation; SAM: Step Activity Monitor; SRHI: Self-Report of Habit Index

Amped-PD (experimental arm) or Active Control (control arm). Assessments will include a standard set of motor and non- motor assessments and will be administered at Baseline, Post-Assessment (after 6 weeks of training), and Follow-up (after 2 additional weeks of unstructured training). Figure 1 summarizes the study flow for the protocol.

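### The within-group Repeated Measures ANOVA is gated on Levene's test, which does not check sphericity, and no correction is named, so its F-test can be somewhat liberal (minor)

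*SAP*

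**What the plan says.** The SAP (Statistical Analysis Plan, first paragraph) sets one rule for all parametric methods: normality by Shapiro-Wilk, and "data that meet the assumptions of homogeneity of variances", as judged by Levene. If the rule is not met, "Otherwise, non-parametric statistics will be used".

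For within-group differences (third paragraph), "we will run a Repeated Measures ANOVA or Friedman's ANOVA on absolute values of all primary outcomes across their respective timepoints". The only correction named there concerns the pairwise follow-up tests: "with multiple post-hoc comparisons corrected using Bonferroni adjustments". No sphericity check, epsilon correction, error term for the contrasts or covariance model is given.

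For between-group differences (second paragraph), "we will run a one-way ANOVA or Kruskall-Wallis test to compare change scores at the 6-Week and 8-Week clinical assessments relative to baseline".

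The protocol (Study Design) sets three clinic assessments: one before training, one when the six-week programme ends, and a last one described as "Follow-up (after 2 additional weeks of unstructured training".

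**The concern.** Levene's test compares variances between independent groups. It suits the one-way ANOVA on change scores. The F-test of a one-arm Repeated Measures ANOVA depends on a different condition: with more than two timepoints, the variances of all pairwise differences between timepoints must be equal. Outcomes can have the same variance at every visit, leaving a variance-homogeneity test nothing to detect, and still break that condition because the correlations differ.

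The visit spacing makes this plausible. Weeks 6 and 8 are two weeks apart, while baseline is six and eight weeks from them. If the later pair correlates more strongly, the uncorrected omnibus F-test rejects too often. What is at stake is the nominal level of the within-arm tests on four primary outcomes in each arm and, depending on the error term used, the post-hoc contrasts.

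**Working it through.** **Inputs from the documents.** 44 participants with balanced allocation, so 22 per arm (protocol, Study Design and Randomization); three clinic timepoints. The plan states no error rate, standard deviation or within-person correlation for this analysis, so there is no figure of its own to reproduce.

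**Assumptions.** Alpha 0.05 for the omnibus test (the SAP's phrase "using two-tailed tests with alpha set at 0.05" stands only in the sentence on secondary outcomes), multivariate normal data, equal variances at all visits, no dropout. Correlations are assumed and shown as a range.

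**Epsilon.** For k timepoints, ε = (Σλ)² / [(k−1)Σλ²], where the λ are the k−1 non-zero eigenvalues of the centred covariance matrix. With unit variances, correlation a between baseline and each later visit, and c between weeks 6 and 8: λ₁ = 1 − c and λ₂ = 1 − 4a/3 + c/3.

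- a = 0.4, c = 0.9: λ₁ = 0.100, λ₂ = 0.767; ε = 0.867² / [2(0.010 + 0.588)] = 0.63.
- a = 0.7, c = 0.8: λ₁ = 0.200, λ₂ = 0.333; ε = 0.533² / [2(0.040 + 0.111)] = 0.94.

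**Omnibus type I error**, simulated with n = 22 and at least 40,000 null data sets per pattern:

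| Correlations 0–6 / 0–8 / 6–8 weeks | ε | Uncorrected | Greenhouse-Geisser |
|---|---|---|---|
| 0.6 / 0.6 / 0.6 (sphericity holds) | 1.00 | 5.1% | 4.7% |
| 0.7 / 0.7 / 0.8 | 0.94 | 5.3% | 4.6% |
| 0.6 / 0.6 / 0.8 | 0.86 | 5.7% | 4.7% |
| 0.6 / 0.55 / 0.85 | 0.76 | 6.2% | 4.8% |
| 0.5 / 0.5 / 0.9 | 0.65 | 7.1% | 5.0% |
| 0.4 / 0.4 / 0.9 | 0.63 | 7.4% | 5.1% |

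**Upper bound.** The worst case is ε = 1/(k−1), where the F ratio behaves as F with 1 and 21 df but is compared with the critical value for k−1 and 21(k−1) df.

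- Three timepoints: P(F₁,₂₁ > 3.22) = 0.087.
- Four timepoints: P(F₁,₂₁ > 2.75) = 0.112.

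**Step-monitor outcomes.** Daily steps and moderate-intensity minutes do not follow the 0/6/8-week clinic schedule. The protocol places monitor wear before training, in early training, during follow-up training and after the final visit, so there may be four periods; the SAP does not list them. The table does not apply to these outcomes. The four-timepoint bound does. As an illustration, correlations decaying with time at 0, 1, 6 and 8 weeks (0.6 at a six-week gap) give ε = 0.54 and an error of 8.1%.

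**Post-hoc contrasts.** The nominal level is 0.05/3 = 1.67% each. The variance of a paired difference is 2(1 − r); a pooled error term replaces each by the average of the three.

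- a = 0.4, c = 0.9: true variances 1.2, 1.2 and 0.2, average 0.867. The ratio of true to pooled is 1.38 against baseline and 0.23 for 6 versus 8 weeks. Simulated null rejection is about 4.4% and 0%.
- a = 0.7, c = 0.8: true variances 0.6, 0.6 and 0.4, average 0.533. The ratios are 1.13 and 0.75. Simulated null rejection is about 2.4% and 0.64%.

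With each contrast computed from its own paired differences, the chance of any false rejection stays at or below 4.7% in every scenario simulated.

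**The case against.** Much of the opposing case stands.

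- **A reader might infer that the error rates are wrong as planned.** The documents do not show that. They give no covariance data, the test is nominal under sphericity, and mild patterns such as 0.7/0.7/0.8 add only 0.3 percentage points.
- **A reader might infer that the 6-versus-8-week (retention) contrast could almost never reject under pooled error.** The near-zero rates above are rejection rates when there is no difference; they are not power. For a true difference of 0.5 SD, pooled-error Bonferroni contrasts still reject in about 53% of trials at 0.4/0.4/0.9, 79% at 0.7/0.7/0.8 and 91% at 0.7/0.7/0.9. The contrast is conservative and loses power: at 0.4/0.4/0.9 the expected t falls from 0.5/√(0.2/22) = 5.24 to 0.5/√(0.867/22) = 2.52. It is not disabled.
- **The SAP does not say that a pooled error term will be used.** It does not exclude one either. With ordinary paired tests there is no post-hoc problem.
- **A reader might infer that the main comparison is compromised.** It is not. The randomised comparison is made on change scores between arms, where sphericity plays no part and Levene is appropriate. Naming Levene in a general opening paragraph is not itself an error.
- **Silence is not a plan to omit.** The SAP is four short paragraphs, and software may report an epsilon correction alongside the uncorrected result. Outcomes that fail the gate go to Friedman and do not use this F-test.

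What remains is that the plan names checks for this F-test that miss its distinctive assumption, and does not fix which p-value will be read.

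**Conclusion.** The point holds in limited form. The gate for the within-group Repeated Measures ANOVA does not cover sphericity, and no correction is named. In the assumed patterns for the clinic-visit outcomes, the omnibus type I error is about 5.3% to 7.4% against 5%, with a ceiling near 8.7%. For step-monitor outcomes with four periods the ceiling is near 11%. Contrasts against baseline would be too liberal (about 2.4% to 4.4% against 1.67% in the two patterns worked above) only if a pooled error term were used.

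These sizes rest on 22 complete participants per arm, normal data, alpha 0.05 and assumed correlations. The effect is confined to within-arm tests and leaves the randomised comparison untouched. Importance is minor; this is a cheap improvement.

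**What to change.** In the SAP:

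1. Limit Levene's test to the between-group one-way ANOVA.
2. Apply the Greenhouse-Geisser correction to every within-group Repeated Measures F-test, without a preliminary sphericity test.
3. Compute each Bonferroni-adjusted contrast from that pair's own paired differences. A mixed model with unstructured covariance is an alternative to steps 2 and 3, since it does not need sphericity.
4. List the timepoints that enter the within-group analysis for each outcome, including the step-monitor periods.

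The cost is a few SAP sentences and a software option. The downside is slightly larger within-group omnibus p-values: where sphericity does hold, the corrected test runs a little below 5% (4.7% with three timepoints and 4.2% with four, in simulation).

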- iii. Self-Efficacy of Walking Duration (SEW-D) is a 10-item self-report that will be administered to determine participants' beliefs of their physical capabilities to successfully complete incremental 5-minute intervals (5 to 40 minutes) of walking at a moderately fast pace, with responses made on 11-point Likert scale (0% = not at all confident; 100% = highly confident).
- iv. Geriatric Depression Scale (GDS) is a brief, self-report involving yes/no questions instrument on psychological aspects and social consequences of depression in the elderly. The short form of GDS of 15-items will be used in this study.
- v. Health-related quality of life will be measured by the Parkinson's Disease Questionnaire 39 (PDQ-39)(see Appendix VII: Outcome Measures). The PDQ-39 is a self-report questionnaire that assesses quality of life over the past month across 8 different dimensions. Items are scored based on a 5-point ordinal system with lower scores reflecting better quality of life.
- Walking Activity:
  - Step Activity Monitor: Walking activity will be measured using the StepWatch 4 Activity Monitor (SAM; Orthocare Innovations, Mountlake Terrace, Washington). The SAM is a self-contained, maintenance-free device that combines acceleration, position and timing information to count complete gait cycles (strides) of the user. It is the size of a pager, weighs 38g (roughly the weight of two AA batteries for comparison) and will be attached with self- adhesive straps above the lateral malleolus (where the shin meets the foot) of the participants' less impaired lower extremity. Data from the SAM, which includes measurement of daily step counts and step intensities, will allow us to examine changes in physical activity in response to the intervention. The validity and reliability of the SAM for capturing stride counts has been demonstrated in persons with various neurological disorders including PD (Shepard 1999, Coleman

- 1999, Macko 2002, Salarian 2004, Gaines 2005, Manns 2009, Speelman 2011).

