- General wear instructions and considerations: Participants will be instructed to wear the SAM for 4-11consecutive days depending on the assessment timepoint. The SAM will be worn continuously during all waking hours, expect when bathing, showering, or swimming. The physical therapist will fill out the SAM researcher form to appropriately document the SAM calibration process for each participant. Participants will be given instructions on how to don/doff the device and will be provided with a form to record times the SAM is removed over wear period. The SAM requires no maintenance by the user besides remembering to keep it on. The physical therapist will provide strategies to help the participant remember to put the SAM back on if they do take it off at any time (e.g., if the SAM is taken off at night, place it on a nightstand next to the bed so it is seen in the morning).
- Specific wear schedule for Baseline Assessment: For the Baseline Assessment, the SAM will be worn for 4 consecutive days prior to initiating the intervention (and will continue to wear it for another 7 days during training please see next section 2. Intervention). Participants will be contacted via phone within 24-48 hours following the evaluation session to ensure that they are comfortable with the device and to address any questions or concerns. Furthermore, participants will be notified that they may contact study staff during work hours at any point during the wear period if they experience any technical issues with the SAM or have any questions.
- Operation and data download: Using the manufacturer's software, the SAM will be calibrated by a physical therapist to each participant's gait pattern based on height, typical walking speed, and leg motion. Collected data will be downloaded to a tablet computer, with which manufacturer's software will convert stride counts to step counts and calculate daily step count values. No identifiable information is collected by the SAM.

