Physical therapy check-in call: During the baseline evaluation visit, the research team will ask the participant which time each week is preferred to have a check-in call. This phone call will last approximately 5-10 minutes to check on participant engagement in the walking program, and to provide guidance regarding any questions/concerns and/or any medical/ technical issues. If participants are unable to carry out the walking program 5- days per week, a study staff member will discuss the barriers to implementation (by phone) and suggest ways to optimize adherence to the program (e.g., setting a schedule). A study staff member will also inquire about adverse events during the weekly phone call and ensure that the participant is comfortable with the walking program.

Step Activity Monitoring: After completing 4 days of wear prior to starting training, the participant will continue to wear the SAM for an additional 7 days upon intervention initiation (total of 11 days continuous wear). During training, both the SAM and the shoe sensors of the music-based device can be worn simultaneously on the same side of the body without interfering with a participant's walking and/or increasing the risk for trips/falls. Participants will return the SAM to study personnel via a pre-labeled, addressed envelope to mail following 11 days of continuous monitoring period. The researchers will download the data and will store in a secure server.

Interruptions in training: In the event of unavoidable interruptions in training, booster sessions may be implemented to promote treatment fidelity. For training interruptions that last up to 2 weeks, the participant will continue the program and receive booster sessions at 100% of the time missed. For training interruptions of greater than 2 weeks, the training will be restarted after a reasonable washout interval, as determined by the Principal Investigator (a licensed physical therapist). If training interruption resulted in permanent change in eligibility, the participant will be withdrawn from the study.

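### Four primary outcomes are compared between arms at two timepoints with no primary timepoint, success rule or adjustment, so the family-wise error of the randomized comparisons is not controlled

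*SAP*

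**What the plan says.** The SAP is one short section, Statistical Analysis Plan. Its between-group paragraph opens with "To examine between-group differences for all primary outcomes (moderate intensity minutes, daily steps, stride time variability, and habit strength" and plans a one-way ANOVA or its rank-based counterpart to "compare change scores at the 6-Week and 8-Week clinical assessments relative to baseline". All four outcomes stand as equals, and so do both timepoints.

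The next paragraph covers change over time within each arm, "with multiple post-hoc comparisons corrected using Bonferroni adjustments". This is the only multiplicity provision in either document.

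A significance level appears once, in the sentence on secondary outcomes: "using two-tailed tests with alpha set at 0.05". None is stated for the primary outcomes.

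Two of the four primary outcomes come from the same device. The Protocol (First Evaluation Visit, Walking Activity) says: "Data from the SAM, which includes measurement of daily step counts and step intensities". The Protocol adds no primary timepoint, ordering of outcomes, success rule or multiplicity plan.

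**The concern.** The comparisons that carry the randomized evidence are the between-group tests, and these have no protection against multiple testing. The correction that is planned applies to comparisons over time within an arm, which do not compare Amped-PD with Active-Control.

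Each test may hold its own error rate, but the documents do not say what pattern of results would count as a positive trial. If one significant result among several is enough, the chance of a false primary finding is well above 5%. If all four outcomes must succeed, there is no inflation across outcomes. A reader of the results could not tell which standard had been intended, or whether 6 or 8 weeks was meant to decide.

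**Working it through.** The plan gives no family-wise error rate, power or sample-size calculation, so there is no figure of its own to reproduce.

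**Inputs from the documents**
- Primary outcomes: 4; timepoints: 2 (SAP).
- Sample size: 44 (Protocol, Study Design), with balanced allocation to two arms (Protocol, Randomization). This gives 22 per arm before dropout.

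**Assumptions**
- Two-sided 0.05 per primary test, borrowed from the secondary-outcome sentence.
- Any one significant result counts.
- Correlations as shown below; the documents give none.

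**Number of tests**
- Plain reading: 4 × 2 = 8.
- If each step-monitor outcome has one post-baseline comparison: 2 × 1 + 2 × 2 = 6.
- If one timepoint is named: 4.

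**Upper reference, independent tests** (1 − 0.95^k)
- k = 8: 1 − 0.95^8 = 0.337
- k = 6: 1 − 0.95^6 = 0.265
- k = 4: 1 − 0.95^4 = 0.185
- Eight tests, Amped-PD direction only: 1 − 0.975^8 = 0.183

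Independence is unlikely, because the 6- and 8-week change scores subtract the same baseline. With equal variances and a common correlation r among the three visits, their correlation is (1 − r) / [2(1 − r)] = 0.5 from that source alone.

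**Correlated tests.** Simulation with no true difference: 22 per arm, normal change scores, pooled t test (the same as a two-group one-way ANOVA).

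| Structure | Tests | Either direction | Favouring Amped-PD |
|---|---|---|---|
| Step-monitor pair 0.8, other pairs 0–0.4, timepoints 0.5–0.9 | 8 | 21–29% | 11–15% |
| Same | 6 | 19–24% | 9–12% |
| Same, one timepoint only | 4 | 15–17% | about 8–9% |
| Every correlation 0.9 | 8 | 12% | 6% |
| Independent | 8 | 34% | 18% |

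Using Kruskal-Wallis instead of ANOVA (normal data, other pairs 0.2, timepoints 0.5–0.9) gives 23–28% for eight tests, so the choice of test does not matter here.

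**Effect of the fix.** Holm's procedure on four tests at one timepoint gave a family-wise error of 2.7–5.0% with no true difference, depending on the correlation.

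**Power cost.** Noncentral t, 42 degrees of freedom, noncentrality d × √(22/2).
- At 0.05 (critical t 2.018), d = 0.865 gives 2.869 and 80% power.
- At the first Holm step, 0.05/4 = 0.0125 (critical t 2.610), the same d gives 60% power. Restoring 80% needs d = 1.046.
- With all four effects at d = 0.865, Holm's power per outcome is about 70%, because later steps use larger levels. With only one true effect it is about 60%.
- Requiring all four to be significant at 0.05, with all four effects at d = 0.865, gives 41% power at outcome correlation 0, 55% at 0.5 and 70% at 0.9.

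**The case against.** The percentage is conditional. It rests on a borrowed alpha, an assumed rule that any one result suffices, and correlations that the documents do not give. In a 44-person trial one could also report four distinct constructs as four separate questions, each at its own level. This stands as a limit on the size. The gap itself does not depend on it: the plan does not say that the outcomes are to be read separately, and even the most favourable case computed (12%) is more than twice 5%.

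The count may also be six. The SAP's within-group paragraph allows outcomes to have their own timepoints, and the step-monitor periods do not line up cleanly with a 6-week assessment. This stands, and both counts are shown.

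Three stronger readings are tempting, and the documents do not support them.
- A reader might infer a false-positive rate of 34%. That requires eight independent tests, which the shared baseline and shared device make unlikely.
- A reader might infer that the trial will claim success on any single result. No claim rule is written, in that direction or any other.
- A reader might infer that the plan ignores multiplicity altogether. It does not; its correction is attached to the within-group comparisons.

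The unclear step-monitor schedule is a measurement question and should not be counted as part of the error inflation. Part of the Follow-Up Walking Program section also breaks off mid-sentence in the text available here, so clarifying wording may have been lost.

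**Conclusion.** The concern holds in this form: the between-group tests of the four primary outcomes have no primary timepoint, success rule or adjustment, so their family-wise error is not controlled. Under the stated assumptions it is about 21–29% for eight tests or 19–24% for six, with extremes of about 12–34% for eight. About half of this falls in favour of Amped-PD. These figures illustrate what follows if any one result counts; they are not properties that the documents fix. Naming a timepoint alone would not be enough, since four unadjusted tests still give about 15–17%. This is an inexpensive improvement to the plan and does not by itself invalidate the design.

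**What to change.** Before any outcome data by arm are seen, amend the SAP to:
1. name one primary timepoint for the between-group comparison;
2. test the four primary outcomes at that timepoint with Holm's procedure at two-sided family-wise 0.05, which also supplies the missing primary alpha;
3. label the between-group tests at the other timepoint secondary;
4. state that efficacy claims rest on the between-group tests.

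A single primary outcome, or a rule that all four must succeed, would also close the gap if tied to the named timepoint. Holm is suggested because it keeps all four outcomes primary.

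The multiplicity change needs no new measurement. It costs power, as computed above: from 80% to about 60% at d = 0.865 if only one outcome has an effect. The other timepoint would support no confirmatory claim. A single primary outcome keeps 80% but demotes three outcomes.

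Separately, the step-monitor wear text must be reconciled. Before training, "the SAM will be worn for 4 consecutive days prior to initiating the intervention". In early training the text says "the participant will continue to wear the SAM for an additional 7 days upon intervention initiation", while the headings of both arms' Remote Walking Program Descriptions give 4 days. After the 6-week visit the text says "The SAM monitor will be given to the participant to wear for 7 days during Follow-Up Training", while the Follow-Up Walking Program heading gives 4 days. A further 4 days follow the final visit, at which the Amped-PD arm returns the device. No wear is described at the end of the structured program. The SAP should say which described period supplies each step-monitor timepoint. That is more than wording: the choice decides whether the comparison concerns structured training, self-managed walking, or walking after the device has been returned.
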